**Study Principal Investigator:**

[name]

Department of Pediatrics

[name]

[name]

[contact]

email: [contact]

Study Title	Encouraging Healthy and Sustainable Dietary Substitutions
Funder	National Heart, Lung, and Blood Institute
Clinical Phase	NA
Study Rationale	
 
The foods people eat have major implications for both human health and environmental sustainability. Approximately 20% deaths in the US are attributed to unhealthy diet and more than 30% of all anthropogenic greenhouse gas emissions are caused by food production.
 
Recently, researchers have identified four simple dietary substitutions that are healthier (i.e., they would improve diet quality and thus reduce risk of diet-related disease) and more environmentally sustainable (i.e., they would reduce carbon emissions associated with food production): replacing beef or pork entrees with chicken or vegetarian entrees; replacing juice with whole fruit; replacing dairy milk with non-dairy alternatives like soy or almond milk; and replacing sugar-sweetened beverages with water.
 
However, it remains unknown how to encourage people to adopt these healthy and sustainable dietary substitutions. Messages about health, the environment, or both health and the environment could encourage these substitutions, but limited research has tested these messages against one another.
 
Emerging adults merit special attention in research on healthy and sustainable dietary substitutions because they have worse dietary quality than older adults and because their dietary behaviors track into later adulthood.
 

Study Objective(s)	
Primary
 
 
To evaluate whether health, environment, or health + environment messages elicit higher perceived message effectiveness than control messages.
 
 
Secondary
 
 
To evaluate whether health, environment, or health + environment messages elicit higher perceived message effectiveness than one another.
 

Study Design	Randomized experiment.
Subject Population	
Inclusion Criteria
 
 
1. Age 18-25
 

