key criteria for Inclusion and Exclusion:	
2. Reside in the United States  3. Able to complete a survey in English
 
Exclusion Criteria
 
 
1. Under the age of 18 or over the age of 26
 
2. Reside outside of the United States
 
3. Unable to complete a survey in English
 

Number of Subjects	1,600
Study Duration	Each subject's participation will last approximately 10 minutes. The enrollment period is expected to last ~1-2 weeks.
Study Phases	
There are two phases:
 
 
(1) Screening: screening for eligibility and obtaining consent and
 
(2) Intervention: study intervention/experimental treatment.
 

Efficacy Evaluations	The primary outcome is perceived message effectiveness for encouraging healthy and sustainable dietary substitutions. It will be measured with 4 items adapted from prior studies.
Statistical and Analytic Plan	
Primary outcome
 
 
• We will use linear mixed models to examine the effect of each intervention topic (health, environment, or health + environment) on perceived message effectiveness compared to the control.
 
 
Secondary outcomes
 
 
• We will use linear mixed models to examine the effect of each intervention topic on perceived message effectiveness compared to the other intervention topics.
 

Data and Safety Monitoring Plan	
 
• The principal investigator is responsible for data quality management and ongoing assessment of safety.
 

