## **Introduction**

The goal of the analyses described here is to use data we collected through an online randomized experiment to examine consumer responses to different messages about healthy and sustainable dietary substitutions. This analysis examines the effect of different message topics (control vs. health vs. environment vs. health + environment) on perceived message effectiveness for encouraging the healthy and sustainable dietary substitutions. This analysis plan pre-specifies the analyses before collecting data and therefore serves as our ex-ante planned analysis.

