## **Objective**

The objective of this study is to examine the effect of message topic on perceived message effectiveness for encouraging healthy and sustainable dietary substitutions. We will compare dietary substitution messages focused on health, the environment, both health + environment, or a control topic. We hypothesize that messages about health, the environment, or both health + environment will receive higher perceived message effectiveness ratings than messages about the control topics.

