## **Statistical Considerations**

### **General Principles**

We will use a two-sided critical alpha of 0.05 to conduct all statistical tests. All confidence intervals presented will be 95% and two-sided. Analyses will include all randomized participants according to experimental conditions they were randomized to (i.e., intent-to-treat). Participants will be prompted to respond to all survey questions before they can continue, so we expect there will be minimal missing data and therefore plan to use complete case analysis.

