### **Statistical Analyses**

We will run separate analyses for each of the 4 experiments (i.e., for each of the 4 dietary substitutions). For each experiment, we will conduct the following analyses:

1. First, primary analyses will use mixed effects linear regression models to **examine whether the intervention *topics* receive higher PME ratings than the control *topic*.**

We will regress PME on indicator variables for the experimental arms (health, environment, or health + environment, treating the control as the referent group). The coefficients on the indicator variables for the intervention topics are average differential effects (ADEs) indicating the difference in mean PME between the intervention topic messages and the control topic messages. Our hypothesis will be supported if the coefficients on the indicator variables for the intervention topics are positive and statistically significant. For these planned primary analyses, we will not correct *p*-values for multiple comparisons.

2. Second, secondary analyses will use mixed effects linear regression models to **examine whether the intervention *topics* receive different PME ratings than one another.** We will use the same model as in (1) to compare the ADEs for each intervention topic to one another using Chi-Squared tests. These analyses will correct *p*-values for multiple comparisons using the Bonferroni-Holm procedure, considering 3 tests to compare each intervention topic to the others.
3. Third, we will **descriptively rank the messages.** We will estimate mean PME for each message statement and rank those means. These analyses will be descriptive (i.e., we do not plan to perform hypothesis tests).

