## Sample Size and Power

We used G\*Power 4 to estimate sample size needs to detect an effect of the health, environment, or health + environment messages vs. the control messages using a repeated measures ANOVA examining between-subjects factors. We estimated power assuming an alpha=0.05, correlation among repeated measures of 0.5 (a conservative estimate based on prior studies), and 2 repeated measures (reflecting that participants will rate 2 messages for their

assigned topic in each of the 4 experiments). Under these assumptions, a sample size of 400 participants per experimental arm (1,600 participants total) will yield 90% power to detect a small standardized effect of Cohen's  $f=.10$  (or Cohen's  $d=.20$ ) or larger. To our knowledge, there are not similar studies of dietary substitution messages, so we powered to detect a small standardized effect size. The planned sample size will also yield 90% power to detect effects of Cohen's  $f=.11$  (or  $d=.22$ ) or larger for comparing each intervention topic vs. the other intervention topics, assuming an  $\alpha=0.0167$  (i.e., 0.05 divided by 3, to correct for multiple comparisons).

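### Must the primary support rule say whether each, any or all three topic coefficients have to be significant?

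*Combined protocol and SAP*

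**What the plan says.** The Objective section states one hypothesis naming three topics: "We hypothesize that messages about health, the environment, or both health + environment will receive higher perceived message effectiveness ratings" than control messages. The primary objective in the synopsis joins the topics in the same way: "To evaluate whether health, environment, or health + environment messages elicit higher perceived message effectiveness than control messages". Neither sentence says how the three results form a verdict.

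The operational text is in Statistical Analyses. It opens with "We will run separate analyses for each of the 4 experiments" and then lists what is done within each one. Item 1 regresses perceived message effectiveness on three arm indicators with control as referent, defines each coefficient as the mean difference between that topic and control, and gives the rule: "Our hypothesis will be supported if the coefficients on the indicator variables for the intervention topics are positive and statistically significant". It adds that the primary p-values are not corrected for multiplicity.

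Three other places bear on the reading:

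- The Statistical and Analytic Plan row of the synopsis says the models will "examine the effect of each intervention topic (health, environment, or health + environment) on perceived message effectiveness compared to the control".
- General Principles says "We will use a two-sided critical alpha of 0.05 to conduct all statistical tests".
- Sample Size and Power says that "a sample size of 400 participants per experimental arm (1,600 participants total) will yield 90% power" at f = .10, or d = .20, with two ratings per participant correlated 0.5.

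**The concern.** The rule has one hypothesis as its subject and a plural as its condition. If one or two of the three coefficients reach significance, the hypothesis is supported under *any*, not supported under *all*, and supported for some topics under *each*. The Introduction claims full pre-specification ("This analysis plan pre-specifies the analyses before collecting data and therefore serves as our ex-ante planned analysis"), yet nothing tells the reader which of these verdicts applies, so in principle the label could be chosen once the results are known.

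The readings also differ in their operating characteristics. *Any* raises the chance of false support within an experiment. *All* lowers power below the stated 90%. If either were intended, the power statement or the decision not to correct would need a second look.

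**Working it through.** **Inputs.** All come from Sample Size and Power, General Principles and Statistical Analyses: 400 per arm, four arms, two-sided alpha 0.05, two ratings per participant with correlation 0.5, d = .20 (f = .10), three contrasts against a shared control. Equal allocation and the full 400 analysed per arm are assumed.

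**Step 1: reproduce the stated 90%.**

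- Variance of a participant's mean of two ratings, in units of the single-rating variance: (1 + 0.5)/2 = 0.75.
- Standard error of one topic-minus-control difference: sqrt(2 × 0.75/400) = 0.0612.
- Expected z: 0.20/0.0612 = 3.27.
- Power: Φ(3.27 − 1.96) = 90.4%.

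The repeated-measures ANOVA formula agrees. Its noncentrality is N f² m/(1 + (m − 1)ρ). For one topic arm plus control, this is 800 × 0.01 × 2/1.5 = 10.67, giving 90.4%. For the four-arm omnibus test it is 1,600 × 0.01 × 2/1.5 = 21.33, giving 98.2%. The plan's 90% is therefore the power of a single topic-versus-control contrast. The pairing of f = .10 with d = .20 fits this too, because d = 2f holds for two equal groups.

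**Step 2: what the readings would imply.** The three contrasts share the control arm, so with equal arms their correlation is 0.5. Support requires z > 1.96 in the positive direction.

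| True effects (three topics) | *Any* supports | *All* supports | Mixed (1 or 2 of 3) |
|---|---|---|---|
| 0, 0, 0 | 6.3% | 0.16% | 6.1% |
| .20, .20, .20 | 98.6% | 79.0% | 19.6% |
| .20, .20, 0 | 97.0% | 2.5% | 94.5% |
| .20, 0, 0 | 90.4% | 0.5% | 90.0% |

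A one-million-run simulation of the second row also gives 19.6% mixed. For a single named topic, power at d = .20 is 90.4% and false support in the positive direction is 2.5%.

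With equal effects, the mixed share is 47% at d = .10, 44% at d = .15, 4.3% at d = .25 and 0.5% at d = .30. At d = .20, varying the assumed within-person correlation from 0.3 to 0.7 moves it from 13.4% to 25.5%. *All* reaches 90% power at about d = .226.

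**Step 3: which reading the text supports.**

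- *Each*: the synopsis wording about each topic, the definition of every coefficient as its own difference, the uncorrected p-values, and a power figure that is exactly that of one contrast.
- *All*: the plural grammar of the rule, and nothing else. Its joint power of 79.0% does not match the stated 90%.
- *Any*: only the word 'or' in the objective and hypothesis, which equally fits a list of topics tested one by one. A rule that the coefficients are positive and significant does not naturally mean that at least one is.

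**Step 4: the four experiments.** The rule sits inside a list of analyses to be done for each experiment, and the outcome items are tailored to each substitution. No pooled verdict is announced, so no rule for combining experiments is needed. The chance that at least one of four experiments is mixed (58% if independent, 1 − 0.804⁴; 20% if perfectly correlated) describes an event on which the plan bases no decision.

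**The case for a change.** The strongest argument for a change is that reporting every coefficient does not settle whether the hypothesis is called supported, which is what the rule is there to decide. A plan offered as fully pre-specified should not rely on inference from other sections. Mixed results are realistic, since the plan knows of no similar studies and the mixed share rises when effects are smaller than d = .20. One sentence would close the matter.

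Part of this stands. The quantifier is missing, the grammar of the rule taken alone leans towards *all*, and an author could in theory pick a label afterwards.

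The rest is weaker. The figure of about 20% contrasts *any* with *all*, neither of which is the reading the plan supports. Between *each* and *all*, a mixed result means support for named topics against no joint support, which is a difference of summary and not of evidence. The 90.0% and 94.5% figures assume one or two topics with exactly zero effect; there a mixed pattern is the right answer, and the separate coefficients show it. Model, referent, direction, alpha and absence of correction are all fixed in advance, so freedom over a label is not freedom over the analysis.

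**Conclusion.** No change follows. The rule leaves out a word, and the surrounding text supplies it: within each dietary substitution, each topic is judged by its own coefficient at two-sided 0.05. On that reading the stated power is right (90.4% recomputed against 90%), the uncorrected tests are consistent with the claims made, and a mixed result needs no tie-break. Writing the word in would alter no estimate, interval, p-value or sample size.

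This rests on the per-topic reading, on equal arms with 400 analysed in each (the plan gives no rate for its exclusions), and on the plan's correlation of 0.5. It also assumes that the report makes no joint claim. A claim that all three topics beat control in an experiment would have power of about 79% at d = .20, and the plan's 90% should not be quoted for it.

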### **Primary Outcome**

The primary outcome is perceived message effectiveness (PME). We will assess PME with 4 items: 3 items adapted from Baig and 1 item adapted from Jongenelis. The items will be tailored to each of the 4 target dietary substitutions (beef/pork, juice, milk, and sugary drinks), as shown below:

1. *How much does this message discourage you from wanting to [eat beef and pork / drink juice / drink cow's milk / drink sugary drinks]?*
2. *How much does this message make [eating beef and pork / drinking juice / drinking cow's milk / drinking sugary drinks] seem unpleasant to you?*
3. *How much does this message make you concerned about the effects of [eating beef and pork / drinking juice / drinking cow's milk / drinking sugary drinks]?*
4. *How much does this message make you want to [eat chicken or vegetarian options instead of beef and pork, eat whole fruit instead of drinking juice / drink non-dairy milk instead of cow's milk / drink water instead of sugary drinks]?*

Responses options for each item are presented as a Likert-type scale: Not at all (coded as 1); Very little (2); Somewhat (3); Quite a bit (4); A great deal (5). We will average responses to these 4 items to create a PME score for each message, assuming sufficient internal consistency (Cronbach's alpha $\geq$ .70).

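### The analysis model has no stated protection against unequal variances across arms; if control ratings vary less, the topic-versus-topic tests would be mildly liberal

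*Combined protocol and SAP*

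**What the plan says.** All references are to the combined protocol and SAP.

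- **Statistical Analyses, item 1.** For each dietary substitution, perceived message effectiveness (PME) is regressed in a mixed linear model on three arm indicators, with control as referent. On multiplicity: "For these planned primary analyses, we will not correct".
- **Statistical Analyses, item 2.** "We will use the same model as in (1) to compare the ADEs for each intervention topic to one another", by Chi-squared tests, adjusted "using the Bonferroni-Holm procedure, considering 3 tests to compare each intervention topic to the others".
- **General Principles.** "We will use a two-sided critical alpha of 0.05 to conduct all statistical tests". Intervals are 95% and two-sided.
- **Primary Outcome.** PME is the mean of four items scored 1 to 5; the lowest response is listed as "Not at all (coded as 1").
- **Objective.** The hypothesis gives a direction only: the intervention messages "will receive higher perceived message effectiveness ratings than messages about the control topics".
- **Study Protocol.** Each intervention participant sees a random two of three messages per substitution. All control participants see the same two.
- **Sample Size and Power.** "a sample size of 400 participants per experimental arm (1,600 participants total) will yield 90% power" for d=0.20, from a repeated measures ANOVA. The topic-versus-topic calculation uses an alpha of "0.05 divided by 3, to correct for multiple comparisons".

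No section gives a mean or SD for any arm, a variance structure, or the type of standard error.

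**The concern.** A mixed linear model with arm indicators ordinarily assumes the same participant and residual variances in every arm. Two features of this trial make that doubtful. First, the outcome is bounded below at 1 and control is hypothesised to score lower; on a bounded scale, moving from the middle towards an end tends to compress the spread. Second, variation from which messages a participant happened to draw enters participant means only in the intervention arms. That effect is probably small, but it points the same way.

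If control varies less, the pooled variance is too small for contrasts among the intervention topics and too large for contrasts with control. At stake are the nominal error rate of the secondary family, which the plan chose to protect with Holm, and the coverage of the 95% intervals for both kinds of contrast.

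**Working it through.** **Step 1: the plan's power figures.** Inputs from Sample Size and Power: 400 per arm, two ratings, correlation 0.5.

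- Variance of a participant's mean of two ratings, in rating-SD units: (1 + 0.5)/2 = 0.75.
- SE of a difference between two arms: √(2 × 0.75/400) = 0.0612.
- Versus control, d=0.20, alpha 0.05: Φ(0.20/0.0612 − 1.96) = 90.4%.
- Topic versus topic, d=0.22, alpha 0.0167: Φ(0.22/0.0612 − 2.394) = 88.5%.

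Both are within two points of the stated 90%, and both assume one variance for all arms.

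**Step 2: effect of unequal variances.** With two ratings per participant and equal arms, the arm contrasts reduce to contrasts of participant means with a pooled variance. Let that variance be 1 in each intervention arm and v in control. The ratio v is not in the documents; 0.8 to 0.5 is an assumed range.

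- Pooled variance: (3 + v)/4.
- Model SE divided by true SE, topic versus topic: k_T = √((3 + v)/4).
- The same, topic versus control: k_C = √(((3 + v)/2)/(1 + v)).
- Actual size of a nominal 5% test: 2 × (1 − Φ(1.96 × k)).
- Holm family error when all topics are equal: the chance that the largest of the three pairwise statistics exceeds 2.394 × k_T, from the range distribution of three normal means.

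| v | k_T | k_C | Topic vs topic | Versus control | Holm family |
|---|---|---|---|---|---|
| 1.0 | 1.000 | 1.000 | 5.0% | 5.0% | 4.4% |
| 0.8 | 0.975 | 1.027 | 5.6% | 4.4% | 5.1% |
| 0.7 | 0.962 | 1.043 | 5.9% | 4.1% | 5.5% |
| 0.6 | 0.949 | 1.061 | 6.3% | 3.8% | 6.0% |
| 0.5 | 0.935 | 1.080 | 6.7% | 3.4% | 6.5% |

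Simulations of the Holm family at v=0.8 gave 5.1 to 5.3%. Interval coverage is 100% minus the test size: at v=0.5, about 93.3% among topics and 96.6% versus control.

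**Step 3: what v might be.** As an illustration only, let variance be proportional to (mean − 1)(5 − mean).

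- Means 2.5 and 2.3 (d=0.20 if the SD is 1): v = (1.3 × 2.7)/(1.5 × 2.5) = 0.94. The tests run at 5.2% among topics and 4.8% versus control.
- Means 3.0 and 2.8: v = (1.8 × 2.2)/(2 × 2) = 0.99, and 5.03% among topics.
- Means 2.5 and 2.0: v = (1 × 3)/3.75 = 0.80.
- Means 2.5 and 1.5: v = (0.5 × 3.5)/3.75 = 0.47.

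So under this law the range in the table needs a gap of roughly half a scale point to one point.

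**Step 4: the opposite direction.** If the control SD is 1.2 times the intervention SD (v=1.44), the sizes become 3.9% among topics and 6.2% versus control.

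**Step 5: power against control.** At d=0.20 in intervention-SD units, the true SE is √(0.75 × (1 + v)/400), and power with the pooled SE is Φ(0.20/SE − 1.96 × k_C): 90.4% at v=1, 92.3% at 0.8, 94.2% at 0.6 and 95.1% at 0.5.

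**Step 6: the remedy.** In simulation (400 per arm, 20,000 runs), using the variances of the two compared arms restored the nominal level. At v=0.49, size among topics was 7.1% pooled and 5.2% arm-specific; versus control, 3.4% and 5.2%. At v=0.25 the figures were 7.8% and 5.1% among topics, and 2.6% and 4.9% versus control.

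**The case against.** The strongest reply is that the premise is not in the plan. A reader might infer from the 1-to-5 scale and the directional hypothesis that control ratings are expected near the floor, and that the tests therefore are too liberal or too conservative. The documents do not support that: they state a direction, no level and no spread, and the bias changes sign if control varies more. This part of the reply stands, and every figure above is conditional on v.

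A reader might also infer that the Holm protection is undone. It is not: for v from 0.8 to 0.5 the family error is 5.1 to 6.5%, partly because Holm starts at 4.4% here.

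A third tempting inference is that the primary analysis falls from 90% to 87–89% power. That compares the pooled test with a more efficient one at an effect chosen to give 90%, while the bounded-scale mechanism yields such ratios only with gaps far larger than that effect. At d=0.20, a smaller control variance raises power above the planned figure (Step 5).

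It is also fair to say that common variance is the usual default of the named model, not a choice the plan states, and that robust or arm-specific variances would be compatible with its text.

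What the reply does not remove is that the standard error is unspecified in a plan that presents itself as fixed before data collection. Sample Size and Power treats d=0.20 as the smallest effect of interest, not as a forecast, so larger gaps are not excluded. Choosing the standard error after seeing the arm variances would weaken the pre-specification.

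**Conclusion.** The point holds conditionally and is small. The plan uses one model for all four arms and again for the topic-versus-topic tests, without saying how unequal variances would be handled. The size of any bias depends on a variance ratio that the documents do not give, so the tabulated error rates are a range of possibilities and not a prediction.

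The concern falls mainly on the secondary comparisons and the confidence intervals. For the primary contrasts, a less variable control arm makes the tests conservative, so no primary claim gains false-positive risk in that case. The calculations assume equal arms of 400, two ratings per participant, equal variances among the three intervention arms, and a model fitted in its ordinary common-variance form. This is a low-priority, cheap improvement, not a demonstrated error.

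**What to change.** Add one sentence to Statistical Analyses, applying to items 1 and 2: each mixed model will use robust (sandwich) standard errors clustered on participant, and all Wald and Chi-squared tests and 95% confidence intervals will be based on them. An acceptable alternative is to give each arm its own random-intercept and residual variance. Either protects whichever way the variances differ.

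The cost is one software option. With about 400 participants per arm, the small-sample penalty of the robust estimator is negligible. If control is less variable, topic-versus-topic intervals widen slightly: by a factor of 1/0.975 = 1.03 at v=0.8 and 1/0.935 = 1.07 at v=0.5. Intervals against control narrow by similar factors (1/1.027 = 0.97 and 1/1.080 = 0.93). The arm-specific version estimates eight variance parameters (two per arm) instead of two. No change to the sample size is needed.

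### Optional efficiency gain: Shaffer's step-down could replace Bonferroni-Holm for the three topic-versus-topic comparisons, with the same 5% family-wise limit in each experiment

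*Combined protocol and SAP*

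**What the plan says.** The synopsis gives the secondary objective as "To evaluate whether health, environment, or health + environment messages elicit higher perceived message effectiveness than one another". Statistical Analyses says "We will run separate analyses for each of the 4 experiments", so each dietary substitution has its own set of topic comparisons. Item 2 of that section describes the tests: "We will use the same model as in (1) to compare the ADEs for each intervention topic to one another using Chi-Squared tests". The resulting p-values are corrected "for multiple comparisons using the Bonferroni-Holm procedure, considering 3 tests to compare each intervention topic to the others". General Principles sets the level: "We will use a two-sided critical alpha of 0.05 to conduct all statistical tests". Sample Size and Power gives 90% power at f=.11 (d=.22) for topic against topic, at alpha .0167, explained as "0.05 divided by 3, to correct for multiple comparisons". No joint test of the three topics is planned.

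**The concern.** Holm's cut-offs are built for null hypotheses that may be true in any combination. The three here cannot be. They are the pairwise equalities among three arm coefficients from one model, and it is impossible for exactly two of them to be true. Holm's second cut-off, .05/2 = .025, guards against two equalities still being true after one has been rightly rejected, which cannot happen.

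The power at stake belongs to the secondary objective. Concluding that one topic outperforms both others takes two rejections, and the second is where Holm is stricter than the 5% limit requires. The same procedure is applied in all four experiments.

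**Working it through.** **Inputs.** From Sample Size and Power: 400 per arm, 2 ratings per person per experiment, correlation .5, d=.22 and alpha .0167 for topic against topic. From General Principles: two-sided .05. From Statistical Analyses: three tests per experiment, one model.

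**Step 1: reproduce the plan's power.** For a repeated-measures ANOVA with a between-subjects factor, λ = f²·N·m / (1 + (m−1)ρ), with two groups, N=800, m=2, ρ=.5.
- Control comparison, f=.10, alpha .05: λ = .01 × 800 × 2 / 1.5 = 10.67, power 90.4% (plan: 90%).
- Topic comparison, f=.11, alpha .0167: λ = .0121 × 800 × 2 / 1.5 = 12.91, power 88.3% (plan: 90%). Exactly 90% needs f=.1127, which rounds to .11, so the plan's figure is reproduced to rounding.

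**Step 2: standard error.** The mean of two ratings has variance (1 + .5)/2 = .75 in SD² units. The SE of a difference between two arms is √(2 × .75/400) = .0612.

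**Step 3: error control of Shaffer's cut-offs.** The smallest p is compared with .05/3; if it is rejected, each of the other two is compared with .05. Three cases are possible.
- All three equalities true: a false rejection requires some p ≤ .05/3, so the error is at most 3 × .05/3 = .05.
- Exactly one true: it is never tested above .05, so the error is at most .05.
- None true: no false rejection is possible.

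This argument does not depend on the power assumptions.

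**Step 4: where the two procedures part.** The first cut-off is the same. They differ only when the smallest p is at most .0167 and the second smallest lies between .025 and .05. In observed standardized differences, the second rejection needs 2.241 × .0612 = .137 under Holm and 1.960 × .0612 = .120 under Shaffer. Every Shaffer cut-off is at least as large as Holm's, so Shaffer can never reject fewer pairs.

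**Step 5: simulation.** 1,000,000 experiments per scenario, normal arm means with variance .75/400.

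| One topic differs from two equal topics by | Power per true pair, Holm → Shaffer | Both differences found, Holm → Shaffer |
|---|---|---|
| d=.22 | 90.6% → 93.0% | 85.2% → 90.1% |
| d=.20 | 83.7% → 87.1% | 75.5% → 82.4% |
| d=.15 | 55.4% → 60.0% | 41.7% → 50.9% |

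- Evenly spaced means 0, .11, .22: each adjacent pair 35.2% → 42.6%.
- Widely spaced means 0, .22, .44: all three pairs found 89.77% → 89.78%, in effect no gain.
- At least one true difference found, one topic at d=.22: 96.0% under both.
- Family-wise error, all topics equal: 4.4% under both.
- Family-wise error, one true equality: 4.1% → 5.0% at d=.22; 2.9% → 4.7% at d=.15.
- Experiments in which Holm rejected a pair that Shaffer did not: none.

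**The case against.** The strongest reply is that nothing needs repair. Holm over three tests is valid and pre-specified, and it meets the plan's own target: at d=.22 it gives 90.6% per pair when one topic differs from two equal ones, against a stated 90%. That stands, and it is why the point is optional.

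A reader might go further than the documents support in four ways.

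- **That Holm's second step buys nothing.** It is not needed to hold the 5% limit, but it does lower the actual false-positive rate. At d=.15 the false claim that the two equal topics differ occurs in 2.9% of experiments under Holm and 4.7% under Shaffer. The extra power is a trade within the limit, and it applies in each of four experiments with no correction across them under either procedure.
- **That the .0167 in Sample Size and Power is too strict and must be restated.** It is also Shaffer's first cut-off, so the statement remains a conservative figure after the change.
- **That a 2-df joint test at .05 followed by each pair at .05 would serve equally well.** It also controls the error and has higher average power in the scenarios run, but it can lose a pair that Holm rejects. With the third topic midway, the extreme pair needs z² of at least 5.99, against 5.73 under Holm. This occurred in at most 0.6% of simulated experiments. It is rare, but only Shaffer carries the guarantee of never rejecting fewer pairs.
- **That the pattern with the largest gain is the expected one.** The Objective section hypothesizes only that each topic exceeds control. It predicts nothing about differences among the topics.

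**Conclusion.** This is an optional efficiency improvement. At the planned d=.22, with one topic differing from two equal ones, the gain is 93.0 − 90.6 = 2.4 points per true pair and 90.1 − 85.2 = 4.9 points for finding both differences. For both differences it grows to 50.9 − 41.7 = 9.2 points at d=.15. It is confined to the second and third rejections: the chance of at least one rejection is the same, and widely spaced topics gain nothing. The small downside is the rise in actual false positives, always within 5% per experiment.

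The error bound and the guarantee that Shaffer rejects whatever Holm rejects follow from logic alone, given valid pairwise p-values. The power figures assume normality, equal variances, correlation .5, and 400 analyzed per arm with no exclusions.

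**What to change.** In Statistical Analyses, item 2, name Shaffer's step-down procedure in place of Bonferroni-Holm and state its rule: within each experiment, compare the smallest of the three p-values with .05/3; if it is rejected, compare each of the other two with .05; otherwise stop. State that the 5% applies per experiment. Make the change, dated, before any outcome data are seen; if data have been seen, keep Holm. Leave the topic-versus-topic statement in Sample Size and Power as a conservative figure, and do not offer the joint-test-first route as an alternative.

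The cost is a sentence or two of text. No participants, data or new model are needed, and the stated error limit does not change. What is given up is part of the margin by which Holm falls below 5%.
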